Aim #1- (a) Cardiovascular Risk Trajectories (H1): There is no validated CV risk engine developed with a prediabetes population. Therefore, we propose to use the ACC/AHA 10-year pooled CV risk engine to estimate annual rate of change in CV risk as our primary outcome. We will use the lipid equation for patients with lipid data available to calculate CV risk at the index and all post-index visits and, to minimize missing CV risk values, the BMI equation at the index and all post-index visits for the remaining patients. The BMI equation estimates higher CV risk relative to the lipid equation. Because the calculation method will be consistent across all visits within each patient this difference will not bias the estimated rate of change in CV risk. CV risk scores for each patient will be calculated at each primary care visit from the index through the entire follow-up period using available EHR data elements. As depicted in Figure 2 Step A, at each visit we will search for the most recent data elements, looking back over a period appropriate for each risk component (i.e., 12 months for BP values or medications, DM diagnosis, smoking, BMI; 48 months for lipids). H1 will be supported if the annual rate of change in CV risk scores from the index visit through the end of the follow-up period is lower (ie, less increase) among patients in the CDS relative to UC clinics; (b) Modifiable diabetes and CV risk factors (H2): Risk factors needed to calculate the CV risk scores (weight, systolic blood pressure, HDL-c, LDL-c, totalcholesterol, smoking), are extracted from EHR files as in Figure 2 Step A. H2 will be supported if annual rate of change in CV risk component trajectories are lower among patients in the CDS relative to UC clinics; (c) Metformin and statin use (H3): Data to assess drug treatment are from EHR files such as prescribed medications. The presence or absence of appropriate drug use will be assessed at each visit. H3 will be supported if appropriate drug use improves over the follow-up period among patients in the CDS clinics relative to UC patients.

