The years elapsed parameter will estimate the annual rate of change in CV risk and risk factors among patients in UC clinics in the absence of intervention, while the treatment by years elapsed parameter estimates the difference in the annual rate of change among patients in the CDS relative to UC clinics. It is expected that CV risk will decrease, or increase at a slower rate, among patients in CDS relative to UC clinics. Similar patterns of improvement, or slower worsening, are expected for CV risk factors. Finally, the treatment group parameter is expected to estimate more appropriate pharmacologic use among patients in CDS compared to UC clinics.

2.2.6.1 H1 Sample size justification. We conducted a power analysis to estimate theminimum detectable slope of the treatment by time parameter (power=.80, α_2 =.05) given the anticipated sample size (15 CDS clinics, 7-11 providers per clinic * 25 patients per provider = 2625-4125 CDS patients, 3 CVR per patient).. The patient sample size was divided by the design effect, Neff = N / [1 + (n_{clus} – 1) ρ], to approximate the effective independent patient sample size (Neff) implied by clinic intraclass correlations (ICC) of ρ = .001-.02. The CVR sample sizes (Neff patient * 3 CVR/pt) were divided by the design effect implied by a patient ICC=0.80. The resulting effective CVR sample sizes were used to estimate the minimum detectable standardized linear regression coefficient (β_{CDS}) relative to β_{UC} =0. When ICC_{clin}=0.001, the minimum detectable β_{CDS} =0.044-0.055; when ICC_{clin}=0.005 β_{CDS} =0.061-0.070; and when ICC_{clin}=0.02 β_{CDS} =0.103-0.108.

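### Keeping one risk equation per patient does not by itself make the H1 slope contrast unbiased: slopes can differ by equation, and the rule does not confine the choice of equation to pre-index lipid data

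*Combined protocol and SAP*

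**What the plan says.** Under Definition and Measurement of Variables, Aim #1 (a), the primary outcome is the annual rate of change in ACC/AHA 10-year CV risk. The plan will use "the lipid equation for patients with lipid data available to calculate CV risk at the index and all post-index visits", and the BMI equation for everyone else, so that few risk values are missing. Lipids are searched for over the previous 48 months.

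The plan grants that "The BMI equation estimates higher CV risk relative to the lipid equation". It then reasons that, with the method constant within each patient, "this difference will not bias the estimated rate of change in CV risk".

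The H1 model (Aim 1 Analytic Approach) has fixed effects for arm, years elapsed, arm by years elapsed, and the index value of the outcome. It has no term for equation and none for equation by time. The link function is left to depend on the distribution of the outcome. No sensitivity analysis by equation is described.

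**The concern.** There are two gaps in the plan's argument.

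**Scale.** If the BMI equation multiplies risk, it multiplies the slope as well. Suppose the lipid equation moves from 10% to 11% in a year. An equation reading 1.25 times as high moves from 12.5% to 13.75%, which is 1.25 points instead of 1. Only a purely additive gap leaves absolute slopes alone.

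**Assignment.** The rule is not limited to data that exist at the index visit. On a literal reading, a patient keeps the lipid equation only if a lipid value is current at every scored visit, so retesting after randomisation helps decide the scale of the primary outcome. The Missing data section says a risk factor is absent because nobody assessed it, which makes it a matter of care delivered. Only CDS clinics have the Smartset, which groups tests with diagnoses and medications (Step E). Patients with untested LDL can be eligible.

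If CDS clinics retest more, the UC arm holds more BMI-equation patients. With risk rising over time, UC then looks steeper and the contrast favours CDS without any real effect.

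A second distortion runs the other way. The BMI equation is there for patients without lipid data, so it takes no lipid input. A lipid improvement in those patients cannot reach the primary outcome, and a true effect is diluted.

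**Working it through.** **The plan's own yardstick.** The documents give no figure for this effect. The only H1 figure is the minimum detectable standardised slope in section 2.2.6.1. With 7 providers per clinic: N = 15 × 7 × 25 = 2625, 175 patients per clinic, clinic ICC 0.001. Neff = 2625 / (1 + 174 × 0.001) = 2236. Effective CVR values = 2236 × 3 / (1 + 2 × 0.80) = 2580. β = (1.96 + 0.84) / √2580 = 0.055, as stated. The ICCs 0.005 and 0.02 give 0.070 and 0.108, also as stated. With 11 providers I get 0.046, 0.063 and 0.103 against the stated 0.044, 0.061 and 0.103. The small differences do not affect this point.

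**When can a lipid value expire?** From the documents: look-back 48 months, follow-up 26-38 months (expected median 32). A value expires during follow-up only if, at index, it is older than 48 − 38 = 10 to 48 − 26 = 22 months; at 32 months of follow-up, older than 16. The hypotheses quote a 24-month median; on that figure the cut-off is 24 months and the effect is smaller.

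**Gap in BMI-equation share (literal reading).** Assumptions, since the documents give no inputs:
- every patient has an index lipid, with age uniform over 0-A months, A = 24 or 48;
- retests occur at random at rate r per year;
- follow-up is F = 32 months = 2.67 years;
- visits occur at random at λ = 3 per year (the eligibility section's median of 6 in 24 months).

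A patient falls to the BMI equation if a visit occurs after expiry and before any retest. For a lipid expiring at s years the probability is

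e^(−rs) × λ/(λ+r) × [1 − e^(−(λ+r)(F−s))],

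averaged over lipid age, with zero for lipids that do not expire. Gaps are taken before rounding:

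| Lipid age at index | r = 0.4 | r = 0.5 | r = 0.8 | Gap 0.4 vs 0.8 | Gap 0.4 vs 0.5 |
|---|---|---|---|---|---|
| 0-24 months | 7.2% | 5.7% | 2.8% | 4.5 points | 1.5 points |
| 0-48 months | 33.6% | 29.7% | 20.9% | 12.7 points | 4.0 points |

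If index lipids are at most 12 months old, 12 + 32 = 44 < 48, none expires and the gap is 0.

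Visits exactly every four months give somewhat more. For 0-24 months the share is (e^(−28r/12) + e^(−32r/12))/6, a gap of 12.3 − 4.6 = 7.7 points for 0.4 vs 0.8. For 0-48 months it is the sum of e^(−rk/3) for k = 1 to 8, divided by 12, a gap of 38.3 − 24.0 = 14.3 points.

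**False contrast.** Contrast = (BMI share in CDS − BMI share in UC) × (BMI slope − lipid slope). As a fraction of the lipid-equation slope this is gap × (slope ratio − 1). With an assumed ratio of 1.2-1.5:
- 0.4 vs 0.8 per year: 0.045 × 0.2 = 0.9% to 0.127 × 0.5 = 6.4%;
- 0.4 vs 0.5 per year: 0.015 × 0.2 = 0.3% to 0.040 × 0.5 = 2.0%;
- evenly spaced visits, 0.4 vs 0.8: 0.077 × 0.2 = 1.5% to 0.143 × 0.5 = 7.1%.

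**Null simulation.** No treatment effect; 17 clinics per arm, 110 patients per clinic, 3 visits, BMI equation as a multiple of the hazard, BMI share 37% UC against 28% CDS, 400 replicates. Relative to assigning the equation at index on the same draws, the literal rule shifted the contrast by −0.013 points per year at a multiple of 1.25 and −0.024 at 1.5. The UC slope was 0.87-0.92 and the standard error of the contrast about 0.04. Type I error was about 0.06 and 0.10 (Monte Carlo error about 0.011); only the second is clearly above 0.05. Across all scenarios, index-only assignment gave 0.035-0.058.

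**Against the yardstick.** Assume an SD of CV risk of 8-12 points, an SD of time of 0.8 years, lipid-equation slopes of 0.5-1.0 points per year, slope ratios of 1.1-1.5 and share gaps of 2-20 points. The bias then runs from under 1% to about 23% of the minimum detectable slope, mostly under 5%.

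**The case against.** The strongest reply concerns the reading. In the parallel clause for the BMI equation, the visit phrase plainly says when the equation is applied. The lipid clause can be read the same way: patients with lipid data are scored by the lipid equation at every visit. This stands as far as it goes. The plan never says when availability is judged, so the looser reading leaves the rule open and does not exclude post-index testing.

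Second, the arm imbalance is an assumption. No document gives testing rates, lipid ages or BMI-equation shares, and no lipid-retest prompt is described; the Smartset only groups tests. This stands in full. With equal shares there is no false contrast.

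Third, the slope ratio is inferred, because the plan says only that BMI-equation risk is higher. An additive gap would do no harm, and a log link would remove a proportional one. The plan commits to neither.

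Fourth, lipids and statin use are tested separately under H2 and H3. That is true, but it does not restore a lipid benefit to the primary outcome.

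A reader might infer that patients change equation mid-course. The plan rules this out: one equation covers all of a patient's visits, and post-index testing can affect only which one. A reader might also infer that the trial's H1 result is wrong. The documents do not support that. The protocol reports a lack of efficacy, and a bias in the direction computed here would favour CDS, so it would not explain that finding.

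**Conclusion.** The no-bias statement is unsupported. Within-patient consistency does not equalise slopes across equations, the assignment rule does not exclude post-randomisation data, and the model has nothing to absorb the difference. Bias in the H1 contrast needs two conditions together: a BMI-equation share that differs by arm, and slopes that differ by equation on the analysed scale. Both are plausible; neither is shown.

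Under the stated assumptions the false contrast is about 1-6% of the lipid-equation slope with retesting doubled. It is 2% or less with 0.4 vs 0.5 retests per year, and zero with recent index lipids at the median follow-up. It is probably small. Dilution of a true lipid effect among BMI-equation patients is a separate limitation that does not depend on imbalance; its size cannot be computed from the documents. This is a correctable weakness in the definition of the primary outcome and should be repaired.

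**What to change.** 1. Assign each patient's equation from data available at the index visit only, and keep it for all visits. Patients without a usable index lipid stay on the BMI equation even if tested later.
2. Add equation type and equation by years elapsed as fixed effects in the H1 model. Once assigned at index, equation type is a baseline covariate.
3. For lipid-equation patients with no lipid inside the look-back at a later visit, carry the last lipid value forward so that no score is lost to a lack of testing.
4. Report the BMI-equation share by arm.
5. Run H1 with the BMI equation for everyone as a sensitivity analysis, noting that it cannot show lipid benefit.
6. Delete the statement that the difference between equations will not bias the slope.

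The cost is two model terms, one table row and one extra run on data already extracted. The downside is that some lipid-equation visits will rest on a value older than 48 months. If H1 has already been analysed, report the revised analysis beside the planned one, not in its place.

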from organizational leaders, providers, and patients to better understand the facilitators and barriers to implementation and to guide refinements of the CDS.

Group-Randomized Study Eligibility Criteria

Study Sites: The group-randomized controlled study will be implemented in 34 Essentia Health primary care clinics in Minnesota, North Dakota, and Wisconsin. Essentia clinics have used the Epic® EHR since 2004 and have, on average, 14 PCPs (range: 1-56) and 377 prediabetes patients at high CV risk per clinic. Eighty-four percent of the Essentia geographic service area is rural, with 56% of the patient population and 66% of clinics located in this rural area. Average household incomes are less than \$35,000 for 42% of patients, and 45% live in health professional shortage areas.

Study Participants: PCPs and Patients: To participate, PCPs must practice at one of the 34 Essentiaclinics and meet these eligibility criteria: (a) be an adult-care general internist, family physician, non-obstetric nurse practitioner, or physician assistant, and (b) provide ongoing primary care for 15 or more prediabetes adults ages 18-75 with high CV risk. There are currently 441 eligible PCPs which should ensure a more robust understanding of implementation barriers and facilitators in a large PCP community.

To be considered for inclusion in primary or secondary analyses, **patients** must meet all the following eligibility criteria at the time of their indexvisit: (a) be 18-75 years old, (b) have no evidence of diabetes in the previous 12 months (based on lab values, diagnosis codes, use of medications, or on problem list), (c) not be pregnant (d) have the most recent fasting plasma glucose of 100-125 mg/dL or HbA1c 5.7-6.4% within the prior 24 months, (e) have the most recent BMI $\geq 25 \text{ kg/m}^2$, (f) have at least one of the following uncontrolled CV risk factors: current smoking, a diagnosis

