of hypertension with index visit BP ≥140/90 mm Hg or no diagnosis of hypertension but two consecutive BP ≥140/90 mm Hg, or ACC/AHA 10-year CV risk ≥7.5% and LDL either untested or ≥70 mg/dL and not on a statin, (g) no hospice care or chemotherapy for cancer within previous 12 months, and (h) have at least one subsequent primary care visit after the index visit. The patient accrual period (for first index visits) will be 12 months, followed by a 26-month observation period. Thus, patients will have 26 to 38 monthsof follow up, with an expected median of 32 months follow up after the index visit. Pilot data indicate that non- pregnant eligible adults have a median of 6 primary care visits over a 24-month period, ensuring broad inclusion in the analysis. We conservatively estimate an average of 25 eligible patients per consented study PCP with few losses due to death (<1%) in the study period. Few patients switch primary care clinics in Essentia and we accurately match over 98% of patients to a regular PCP. Ultimately, after accounting for all eligibility criteria, we anticipate over 6,600 eligible patients for Aim 1 and Aim 2 analyses. For Aim 1 and Aim 2 analyses we will retrospectively collect CV clinical information and will ask for a waiver of patient consent. The IRB has waived consent in prior and existing evidence-based CDS studies. Patients specifically recruited for focus groups and surveys will be consented and receive

modest compensation for those activities.

Description of Usual Care (UC) and PrediabetesCDS Intervention Conditions.

[figure not shown]
UC Condition. UC clinics and their consented PCPs will have no access to the CDS intervention.

Prediabetes CDS System: The Prediabetes CDS intervention is rooted in a series of antecedent studies that have developed successful forms of CDS for diabetes. The process flow of the intervention is shown in Figure 2.Specific steps in implementation of the Prediabetes CDS intervention are described below.

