Step F: Iterative Use of the Prediabetes CDS over a Series of Visits. A key design feature of this intervention is its repeated use at all office visits of eligible patients during the intervention period. The CDS is automatically activated at any visit during the study period for eligible patients and provides updated treatment priorities and recommendations at each visit. Pilot data indicate that eligible patients average 4-6 primary care visits during a 24 month period, assuring that nearly all intervention patients have at least 3 exposures to the CDS. The CDS can also be manually activated by the PCP. In our previous study, almost 70% of eligible PCPs maintained use of the CDS system. With strong support from Essentia leaders and PCP leaders, we expect similar use rates.

Prediabetes patients converting to diabetes will continue to receive appropriate CV risk reduction prioritization and evidence-based glucose and aspirin treatment recommendations, thus facilitating timely treatment transition for newly diagnosed diabetes and reducing the lag time often reported between conversion to diabetes and being clinically diagnosed and treated.

Implementation of the Prediabetes CDS Intervention: Key implementation stages include: organizational engagement; adapting, piloting, and refining the Prediabetes CDS; and implementing the Prediabetes CDS group-randomized study. Key informant interviews, focus groups, surveys, usability testing, EMR data, and continuous quantitative and qualitative feedback between researchers and stakeholders will be used to monitor the implementation process and outcomes.

Organizational Engagement: As part of the initial engagement process, Essentia leaders and PCP leaders have already provided letters of support for the prediabetes CDS. Further engagement with Essentia leadership, informatics personnel, and key providers will occur through in-person meetings, conference calls, informational meetings, and identification of critical personnel to participate in the development, adaptation, and piloting processes of this study.

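### A recorded diabetes diagnosis can expire under the rolling 12-month look-back, so a converter may be scored non-diabetic again and the primary risk score falls artificially (probably a small effect, of unknown direction between arms)

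*Combined protocol and SAP*

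**What the plan says.** Under Definition and Measurement of Variables, Aim #1 (a) (H1), the score is calculated at every primary care visit from index to the end of follow-up: "at each visit we will search for the most recent data elements, looking back over a period appropriate for each risk component". The windows are "12 months for BP values or medications, DM diagnosis, smoking, BMI; 48 months for lipids". The look-back is repeated at each visit, so it rolls forward with the patient.

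Other parts of the plan bear on this:

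- **Eligibility (Study Participants).** At index every patient must "have no evidence of diabetes in the previous 12 months (based on lab values, diagnosis codes, use of medications, or on problem list".
- **Follow-up (Study Participants).** "The patient accrual period (for first index visits) will be 12 months, followed by a 26-month observation period"; hence "patients will have 26 to 38 monthsof follow up, with an expected median of 32 months follow up after the index visit".
- **Converters (Step F).** "Prediabetes patients converting to diabetes will continue to receive appropriate CV risk reduction prioritization and evidence-based glucose and aspirin treatment recommendations". No section removes or censors them.
- **Model (Aim 1 Analytic Approach).** All available index and post-index scores enter the H1 model.
- **Definitions.** The H1 text does not say which records make up a diabetes diagnosis for scoring. Measurement detail is assigned to Appendix A, which is not in the supplied text.

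**The concern.** A one-year window suits quantities that go stale, such as a blood pressure reading. Applied to a diagnosis, it means that the absence of a recent record is read as the absence of disease. A patient who converts, is recorded once and then has no qualifying record for a year moves from diabetic to non-diabetic in the score. The score steps down at the next visit although nothing about the patient has changed.

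This differs from the question of when diabetes is first detected, because here a diagnosis is lost after it has been recorded. The Missing data section does not cover it: a lapsed diagnosis yields a wrong value, not a missing one. The plan also defends its mix of lipid and BMI equations on the ground that the method is the same across a patient's visits. A component that can switch on and then off through recording gaps weakens that within-patient consistency.

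At stake is the accuracy of the primary slope in each arm and, if lapses differ by arm, the H1 contrast.

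**Working it through.** **1. The plan's follow-up figures.** The last patient enrolled has 26 months and the first has 26 + 12 = 38. The median under uniform accrual is 26 + 6 = 32. All three agree with the plan.

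**2. Can a diagnosis expire during follow-up?** It must be recorded at least 12 months before follow-up ends: by month 26 - 12 = 14, 32 - 12 = 20 or 38 - 12 = 26. So it can.

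**3. Is an empty window scored as non-diabetic?** Every patient has no diabetes evidence in the 12 months before index, yet an index score is computed. An empty window therefore means no diabetes. The same rule at a later visit gives the same result.

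**4. Size within an arm.** These inputs are assumptions, because the documents give none of them: conversion 5-10% per year; 5-15% of patients who convert early enough lapse; a diabetic score of 15%; a diabetes multiplier of 1.5-2.

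- Step when the diagnosis lapses: 15 - 15/1.5 = 5 points; 15 - 15/2 = 7.5 points.
- Converted by month 20 (1.67 years): 1 - 0.95^1.67 = 8%; 1 - 0.90^1.67 = 16%.
- Patients affected: 8% × 5% = 0.4%; 16% × 15% = 2.4%.
- Mean false fall at 32 months: 0.4% × 5 = 0.02 points; 2.4% × 7.5 = 0.18 points.
- Per year (÷ 2.67): about 0.01 to 0.07 points.

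The cut at month 20 matters because later diagnoses cannot expire by month 32. The hypotheses state a median of 24 months, not 32. On that figure only conversions by month 12 count: 5-10% × 5-15% = 0.25-1.5% of patients, then × 5-7.5 points ÷ 2 years = 0.006-0.06 points per year, which is of the same order.

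**5. Is a 5-15% lapse rate plausible?** Step F says "eligible patients average 4-6 primary care visits during a 24 month period", or 2-3 per year. If each visit independently carries a diabetes code with probability c, the chance of no code in a 12-month span with v visits is (1 - c)^v:

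| c (assumed) | v = 2 | v = 3 |
|---|---|---|
| 0.3 | 49% | 34% |
| 0.5 | 25% | 12.5% |
| 0.7 | 9% | 2.7% |
| 0.9 | 1% | 0.1% |

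A rate of 5-15% corresponds roughly to coding at 50-70% of visits.

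**6. Simulation cross-check.** Assumed inputs: non-diabetic risk 15%, drift 0.5 points per year, 2.5 visits per year, conversion 6% per year, and a hazard ratio of 1.6 for diabetes, so that diabetic risk is 1 - 0.85^1.6 = 22.9%, a step of 7.9 points. There were 30,000 patients per scenario, analysed by least squares on within-patient-centred visit times, without clinic clustering. With the diagnosis carried forward, the slope is 0.968 points per year. Under the 12-month rule:

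| Re-coding per visit | Slope | Understatement (before rounding) | Converters ever reverting |
|---|---|---|---|
| never | 0.744 | 0.224 | 43% |
| 30% | 0.893 | 0.076 | 21% |
| 50% | 0.934 | 0.035 | 11% |
| 80% | 0.961 | 0.007 | 3% |

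Across conversion of 3-10% per year, the understatement runs from 0.003 (80% re-coding) to 0.357 (never re-coded). The large values require converters to be rarely or never re-coded.

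**7. Between arms.** Only the part that differs between arms biases H1. As an illustration at the top-end inputs, a 15% lapse rate in one arm against 10% in the other gives 16% × 5% × 7.5 ÷ 2.67 = about 0.02 points per year.

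**The case against.** The strongest objection is that the data source is undefined. The eligibility criteria accept laboratory values, codes, medications or the problem list as evidence of diabetes, and the covariates section draws comorbidities from diagnosis codes and problem lists. If a standing problem-list entry also counts for scoring, little or nothing expires. If laboratory values or medications count, a lapse requires a year without those as well. This stands as a limit on size. It does not remove the point, because the H1 text names only a diagnosis within 12 months and states no persistence.

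A second objection is that the post-index window matches the 12-month definition used at index. That is so, but index eligibility asks whether a patient may enter, whereas the trajectory needs a status that does not reverse through recording gaps.

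A reader might infer two stronger things:

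- **That Step F treats diabetes as a lasting state for scoring.** It does not. It concerns the recommendations that converters receive and says nothing about the score.
- **That lapses are commoner in usual care, so H1 is biased against the CDS.** Continued prompts could produce more re-coding in CDS clinics. But the plan also expects the CDS to shorten the delay to diagnosis, and an earlier record has longer to age past 12 months, which could mean more expiries in CDS clinics. Equal lapses would mostly understate both slopes. The documents do not settle the direction.

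Finally, carry-forward has costs. A mistaken or rule-out code would persist, and any between-arm difference in detection would remain. The document, dated March 2021, already reports lack of efficacy as the reason for not testing the cost-effectiveness hypothesis, so a scoring change made now would be post hoc and should be labelled as such.

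**Conclusion.** The point holds as a defect in the stated scoring rule. With a rolling 12-month window, no carry-forward and no censoring, a converter without a qualifying diabetes record in a later 12-month span returns to non-diabetic, and the primary score falls artificially.

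The effect is probably small: about 0.01-0.07 percentage points per year within an arm, under the assumed conversion, lapse rate and multiplier shown above. It would be larger only if converters were seldom re-coded, and it largely vanishes if a standing problem-list entry counts. The between-arm effect is some fraction of the within-arm figure, and its sign is unknown. The documents do not support a claim that H1 is materially biased or biased in a particular direction. This is a worthwhile refinement of the primary score, not a threat to the trial's conclusion.

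**What to change.** 1. Take the diabetes diagnosis off the 12-month list for post-index visits.
2. Define a qualifying diabetes record from the sources already named in the eligibility criteria (laboratory values, diagnosis codes, medications, problem list), with a guard against single rule-out codes.
3. Score diabetes as present at every visit from the first qualifying post-index record onward, by the same rule in both arms.
4. Report two sensitivity analyses: one under the plan's 12-month rule, and one with diabetes status held at its index value. The second is needed because carry-forward does not remove a between-arm difference in detection.
5. If the scores have already been analysed, label the re-scoring as post hoc and show it beside the result under the 12-month rule. If problem-list entries were already read without a window, a sentence saying so is enough.

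The cost is a short definition, a small change to the scoring code and two re-runs on EHR data already held, with no new patient contact. The remaining downside is that a wrongly recorded diagnosis persists in the score.
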